Selection of Subjects:

From the parent study, 42 participants will have 2 or more age and/or COVID-19 related social isolation risk factors (Table 2). These individuals will be randomized into the Parent study's WL-Protein arm (n=21) or the WL-Control arm (n=21)

Table 2. High-Risk Criteria Due to COVID-related Isolation (≥ 2)

Criteria	Definition
Isolated living environment	Lives alone or eats all meals alone
Risk of sarcopenia	Score of ≥ 4 on SARC-F screener
Poor access to medical care	$\leq 10\%$ Service connection
Sensory impairment	Hearing and/or visual impairments that impacts IADLs and/or ADLs
Caregiver burden	Caregiver for grandchildren, children, and/or spouse
Chronic pain	Moderate, severe, or very severe response to SF-36 pain question

Randomization: The following variables will be blocked in this order: 1) Race (white versus black, 2) chronic health conditions (≥ 3 versus <3), and 3) physical function, SPPB score (≥ 8 versus <8). An equal number of participants will be randomized across the two arms to end up with N=42.

Arm 1: High Risk Weight Loss Protein (HR-WL-Protein; n = 21 completers) 10% WL diet with 1.4g protein/kg body wt/day; ≥ 30 g high quality protein per meal

Arm 2: High Risk Weight Loss Control (HR-WL-Control; n = 21 completers) 10% WL diet with 0.8g protein/kg body wt/day

Screening (Two-step process):

Screening Visit Level 1: Confirm 2 or more high risk criteria (see Table 2), confirm $\text{BMI} \geq 30 \text{ kg/m}^2$, confirm SPPB score of 4-11, confirm fasting plasma glucose ≥ 95 and $< 126 \text{ mg/dL}$, confirm Mini-Cog ≥ 3 (or ability to complete all ADL's).

Screening Visit Level 2: Routine blood and urine chemistries and confirm age-normal renal status.

Aim 1:

Feasibility: Recruitment, retention, and intervention resources (defined in detail below)

Acceptability (6 months): participant satisfaction of intervention (defined in detail below)

Aim 2:

Physical Performance (0, 3, 6 months): Short Physical Performance Battery (SPPB) including three domains Balance (side-by-side, semi-tandem, tandem), gait speed (4-meter timed walk), and lower extremity strength (chair stands)

Anthropometrics: Body weights and body composition using Bod-pod.

Insulin Resistance: Glycated Hemoglobin (HbA1c), assessed in whole blood.

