This study will utilize a Request for HIPAA waiver of Authorization and waiver or alteration of informed consent process to identify potential participants for this research study. Each year of the study we will use the VA Informatics and Computing Infrastructure (VINCI) to conduct a query to identify Veterans seen at the Durham VAMC in the past year who were age ≥ 55 yrs, were obese ($BMI \geq 30 \text{ kg/m}^2$), and had prediabetes identified by either a HbA_{1c} between 5.7 and 6.4 % or a fasting blood glucose of ≥ 95 to $< 126 \text{ mg/dl}$. We will also work with the MOVE program coordinator, [name], and the Diabetes Management Clinic at the VA, to recruit patients who fit the above description. Finally, we will conduct face to face recruitment at VA organizations within the community and local libraries. We will also provide flyers to various VA clinics for providers and clinic staff to share with veterans. Potential clinics include primary care and specialty clinics at the Durham VA, Hillandale, Raleigh and Wake County, and Clayton clinics.

³ Participants enrolled after 10/1/2023 will have a goal of 5-10% reduction in body weight due to the shortened study period.

We will contact Veterans who meet inclusion criteria by mail via a recruitment letter signed by the PI that describes the study and emphasizes eligibility based on the fact that their prediabetes increases their risk for developing type 2 diabetes. In the letter, potential participants will call our office number and will be given an opportunity to “opt-out” and decline participation and/or further contact regarding participation. Five business days after the mailing, Veterans who have not called the study number to decline participation will be called by a study staff member to request their participation in the research study (see telephone screen script). Following a script, the recruiter will describe the study, query about potential exclusions and assess overall interest in participation. Interested and eligible subjects will then be scheduled for their first screening visit.

Additional recruitment methods include the advertisement of the study via third parties, including Facebook or Instagram, Craigslist, DukeList and Google ads. Advertisements will direct interested participants to contact the study team for more information about the study.

Consent Process

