Power Estimate: The sample size of $n = 84$ per group is based directly on our findings in the MEASUR-UP study, which used the same diet treatments, study population, and primary outcome as in the present Aim 1. In MEASUR-UP, the SPPB score for WL-Pro changed by +2.4 units over the course of the study, while the WL-Control group experienced an increase of +0.9 units. The pooled standard deviation of these changes is 1.7. Thus, the MEASUR-UP study observed a standardized difference of $0.88 = (2.4 - 0.9)/1.7$. Differences of this magnitude have been labeled as 'large' in the power analysis literature. Assuming equivalent effect sizes observed in the MEASUR-UP study, an overall sample size of 100 (evenly divided between groups), and a Type-I error rate of 0.05 (two tailed), the power of our design is greater than 99% to declare significance for the effect size observed in the pilot. At 80% power, this design is powered to detect a difference in change scores in the SPPB of 0.96, or a standardized difference of 0.57.

Analysis Plan for the supplemental protocol:

Aim 1: Feasibility-Recruitment capability: Proportion of participants recruited will be calculated as the number of participants deemed potentially eligible and contacted for enrollment divided by the total number of

participants enrolled. Feasibility of recruitment hypothesis: ≥35% of participants approached for recruitment will agree to participate

Feasibility-Retention: Retention proportion retention will be computed by dividing the number of retained subjects at the end of the intervention by the total number randomized into the study.

Retention hypothesis: ≥80% of participants will remain in the study for the duration of the trial

We will calculate the rate of retention and its respective confidence intervals overall and by group. While non-powerful, we will assess if these rates differ by chi-square test of proportion and Poisson regression respectively. In a series of sensitivity tests, we will assess if retention overall was impacted by demographic and high risk variables.

Feasibility-Intervention Tools: Records of intervention tools and time spent to administer them will be used for post-study analysis of intervention tool effectiveness.

Acceptability-Satisfaction: participant satisfaction of intervention delivery, overall experience, and outcomes will be assessed using a Likert scale and open-ended questions.

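### The supplement's ≥35% recruitment test is about Veterans the study approached, but its ratio counts all enrolled men, including those who answered advertisements, and is printed upside down

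*Combined protocol and SAP*

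**What the plan says.** In the combined protocol and SAP, the analysis plan for the supplemental protocol (Aim 1, recruitment capability) gives both a hypothesis and a ratio. The hypothesis is that "≥35% of participants approached for recruitment will agree to participate". The proportion recruited is defined as "the number of participants deemed potentially eligible and contacted for enrollment divided by the total number of" participants enrolled.

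The Subject Recruitment section describes several routes:

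- **Letter and call.** After a database query and a mailed letter, "Veterans who have not called the study number to decline participation will be called by a study staff member". This is an approach by the study.
- **Clinics and in person.** The team works with the MOVE coordinator and the Diabetes Management Clinic, and "we will conduct face to face recruitment at VA organizations within the community and local libraries". These are also approaches.
- **Flyers.** "We will also provide flyers to various VA clinics for providers and clinic staff to share with veterans". These could be classed either way.
- **Online advertisements.** "Advertisements will direct interested participants to contact the study team for more information about the study". Here the Veteran makes the first move.

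The supplement draws its men from the parent study and the same target population, so these routes apply to it. No section defines approached or contacted, says how a man who answers an advertisement is counted, or splits the rate by source.

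**The concern.** An agreement rate among approached men needs the same men in both parts of the fraction. A man who answers an advertisement was not approached. If he is counted only as enrolled, the numerator includes someone from outside the denominator. If he is counted in both parts, the rate blends volunteers with approached men. Neither version is the quantity in the hypothesis.

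Recruitment is one of the two elements of feasibility named in supplement Aim 1, and it has a numeric mark. Whether that mark is met could depend on how much of the sample came through advertising rather than on how Veterans respond when approached.

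**Working it through.** **Inputs from the documents.** The threshold is 35%. The supplement size is 42: "An equal number of participants will be randomized across the two arms to end up with N=42". The plan gives no expected number approached and no self-referred share, so there is no derivation of the 35% to reproduce. The rates and splits below are assumptions.

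**Notation.** C = men approached; A = approached men who enrol; S = self-referred men who enrol; a = A/C, the rate among approached men; f = S/(A+S), the self-referred share of enrollees; s = the yield among self-referred men. For this arithmetic, agreeing is first taken as enrolling.

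**1. The ratio as printed, C/(A+S).** With 42 enrolled, 35% on the intended scale corresponds to 42/0.35 = 120 approached. The printed ratio is then 120/42 = 286%. It falls below 35% only if C < 0.35 × 42 = 14.7, so it passes almost automatically. Extra self-referred enrollees lower it: with A = 30 it is 120/30 = 400% without them, and 120/42 = 286% with S = 12. The orientation must be corrected first.

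**2. Intended direction, self-referred men in the numerator only.** The scored rate is (A+S)/C = a/(1−f), which reaches 35% at f = 1 − a/0.35.

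| Assumed a | f needed | S of 42 | Check |
|---|---|---|---|
| 30% | 14% | 6 | (36+6)/120 = 35% |
| 25% | 29% | 12 | (30+12)/120 = 35% |
| 20% | 43% | 18 | (24+18)/120 = 35% |

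The arm descriptions call the 21 per arm completers. If 42 is therefore a completer count and retention is the hypothesised 80% ("≥80% of participants will remain in the study for the duration of the trial"), enrolment is 42/0.8 = 52.5, about 53. The shares f do not change.

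**3. Intended direction, self-referred men in both parts.** The scored rate is 1/((1−f)/a + f/s), which reaches 35% at f = (1/a − 1/0.35)/(1/a − 1/s).

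| Assumed a | f needed, s = 70% | f needed, s = 50% |
|---|---|---|
| 30% | 25% | 36% |
| 25% | 44% | 57% |
| 20% | 60% | 71% |

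For example, at a = 25% and s = 70%: (4 − 2.857)/(4 − 1.429) = 1.143/2.571 = 44%. The split of 30 approached and 12 self-referred enrollees, with all the self-referred men enrolling, now scores 42/132 = 31.8% and does not pass; 19 such men would be needed (49/139 = 35.3%). If s is 35% or less, the threshold cannot be reached this way.

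**4. The opposing effect.** The hypothesis concerns agreeing, but the ratio counts enrolling. If enrolled means having passed screening, men who agree and then fail screening lower the rate. For illustration, if 42 of 120 approached men agree (35%) and 6 fail screening, the enrolled rate is 36/120 = 30%.

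**The case against.** The strongest reply has four parts.

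- **The printed formula.** A reader might infer that, as the plan stands, advertising inflates the recruitment rate. The text does not support that: enrolled men are in the printed denominator, so self-referral lowers the ratio. This stands. The inflation exists only for enrolled over contacted, which is the only orientation that makes sense against a minimum of 35%. Correcting the orientation alone would leave the mismatch in place.
- **Counting as contacted.** A man who phones, is judged potentially eligible and is enrolled may well count as contacted for enrolment. The documents do not say. If he does, the smaller effect in step 3 applies. It would be tempting to treat volunteers as almost certain to agree, but nothing supports that. The database query pre-filters on age, BMI and glycaemia, and no such filter is stated for advertisement responders, so their yield could be lower.
- **The share.** Advertisements are listed as additional methods, with no proportion given. At a 10% share and a true rate of 30%, even the less favourable formula gives 0.30/0.90 = 33.3%, which is still short of 35%. Flyers passed on by providers and clinic staff are not clearly self-referral; only the advertisements are.
- **Consequence.** The plan attaches no go/no-go decision to 35% and does not say that a later trial will be sized from this rate. Overall yield across mixed channels is also a legitimate figure to report.

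All four limit the size and certainty of the effect. None makes the ratio a measure of agreement among approached Veterans.

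**Conclusion.** The concern holds as a mismatch between the hypothesis and its measure. The hypothesis names approached men who agree, while the ratio uses all enrolled men and is inverted. Once it is turned the right way up, self-referred men can bring it to 35% when the rate among approached men is lower. This takes 6, 12 or 18 of 42 enrollees (true rates of 30%, 25% or 20%) if they are outside the contacted count, or shares of 25%, 44% or 60% if they are in both counts with an assumed 70% yield.

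The conclusion that the mark will be met falsely does not follow. The self-referred share and yield are not in the documents, and screening failures act in the opposite direction, so the net direction is unknown. The effect is confined to the supplement's recruitment feasibility measure.

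**What to change.** In the edit that corrects the inverted ratio, define both parts on the same men:

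- **Numerator:** potentially eligible Veterans first approached by the study who agree to participate.
- **Denominator:** all potentially eligible Veterans first approached by the study, by letter and telephone, through a clinic, or face to face.
- **Counting rule:** each man is counted once, including across the yearly database queries, and is classed by his first recorded contact. This also settles the man who receives a letter and sees an advertisement.
- **Flyers:** state in advance how responses to them are classed.
- **Separate reporting:** give the enrolled-over-approached yield and the number of self-referred advertisement responders, by source, outside the ≥35% test.

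The participant tracking spreadsheet described under Data and/or Specimen Location already covers screening and needs only a recruitment-source column. The cost is a short change to the analysis plan and that column. The downside is that the reported rate may be less favourable.

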Setting: Screening, baseline, outcome testing and intervention meetings will be conducted at the Sarah W. Stedman Center for Nutritional Studies on the Center for Living Research and Wellness campus at Duke University. Diet and exercise classes will be offered virtually via WebEx or in person at the Center for Living campus. Anthropometrics, functions tests, and blood collection will take place in the Clinical Research Unit there or may be conducted virtually if needed. The Isokinetic knee extension peak torque testing and BodPod body composition measurements will be done in the Sports Sciences Institute, which is adjacent to the Stedman Building. The thigh CT scans will be conducted in Radiology at the Veterans Affairs Medical Center in Durham.

We will enroll participants until we reach a total of 112 study completers. We anticipate enrolling approximately 160, allowing for a 30% dropout rate.

Study Arms:

- **Arm 1: WL-Control (n=56 completers)**
10%* WL diet with 0.8 g protein/kg body wt/day
- **Arm 2: WL-Pro (n=56 completers)**
10%* WL diet 1.4 g protein/kg body wt/day; \geq 30g high quality protein per meal

**Participants enrolled after 10/1/2023 will participate in a shortened study period of 3 months, with only 0 and 3 month assessments for most measures, as noted in the added footnotes below. Their weight loss prescription will be targeted to an expectation of at least 5-10% loss of body weight.*

Measurements:

After the participant has been consented and HIPAA Authorization forms have been signed, screening and baseline assessments will be conducted:

Screening process:

Screening Visit : Consent; confirm BMI ≥ 30 kg/m², confirmed SPPB score of 4-11, confirmed fasting plasma glucose ≥ 95 and < 126 mg/Dl or A1c between 5.7-6.4 (will be confirmed with LapCorp results), and confirmed Mini-Cog score ≥ 3 (if less than 3, confirm participant can conduct all ADLs).

Upon the completion of all baseline assessments (see below), the study biostatistician will then use permuted-block randomization to assign participants to WL-Control or WL-Protein groups. The following variables will be blocked in this order: 1) Race (white versus non-white, 2) Couple/Single status. An equal number of participants will be randomized across the two arms to end up with N=84 (42 black and 42 white) in each arm.

Measures and Data Collection Points

Primary outcome: Physical function (SPPB)

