On the day of the consent meeting, potential participants will be presented a full description of the study measurements, the interventions, and the randomization process. The participant will be told that their participation is voluntary, and they may choose not to answer any questions that they find too sensitive. Also, Veterans will be told that their participation will not affect their care at the VA. The study staff member will explain the study in detail. The participant will be given as long as they need to read through the consent form and HIPAA Authorization. Study staff will answer all questions and concerns. No study procedures will begin until formal, written informed consent has been obtained. This visit will determine if a participant is eligible to participate in the study. If a participant does not qualify, they will be given a letter indicating the reason of disqualification, and other resources/ programs for which they may qualify based on their condition. This visit will take place at the Duke Center for Living and will last approximately 90 minutes.

Adverse Events

All adverse events will be reported per Durham VAMC requirements. Given that the study population is older, somewhat functionally impaired and with metabolic risk factors, and based on our prior experience with a similar (non-Veteran) population, we anticipate that we will have adverse events, including one or more serious adverse events during the study period but that these adverse events will not be associated with the intervention, which is low risk. The most likely adverse event relating to the intervention would be a minor musculoskeletal injury during the exercise class. We will work to prevent this with close supervision by a trained exercise instructor and providing safety guidelines for when exercising at home. All Serious, Unanticipated and Related adverse events will be reported to the IRB within 5 business days of hearing of the event. All other adverse events will be reported at continuing review.

Costs and/or Payments to Subjects

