A number of potential health benefits that may accrue to participants and important scientific knowledge will likely result from this work. Subjects will receive a weight loss intervention that is very likely to produce a modest but metabolically beneficial amount of weight loss and an exercise intervention that will help them be more physically active. Furthermore, we expect that participants will achieve substantial life-style modifications that could be sustained as a part of their personal health regimen in the setting of their community environment. Information collected from this study will benefit others through a greater understanding of how to best maintain muscle function and improve insulin sensitivity while reducing obesity in the older population.

Data and Safety Monitoring

The individuals responsible for data safety and monitoring will be the PI, the Registered Dietitian, the project coordinator, and the study Co-Investigators (Drs. [name], [name], [name], and [name]). Further data safety and monitoring will be provided by the PI. There will be several ongoing mechanisms for monitoring and reporting of adverse events: 1) ongoing participant contact via study personnel, 2) study telephone number provided to participants to report concerns related to study participation; and 3) weekly meetings between the PI and study personnel.

In addition, an internal data safety advisory group will be established to monitor the study and assure that subject safety and confidentiality is being protected. This group will receive annual reports on subject enrollment and regular reports of any adverse events that occur. They will meet with Drs. [name], [name], [name], [name], and [name] on an annual basis for review of study progress and results. The advisory

group will review clinical events to identify any excess event rate in the study population over that expected based upon historical experience. Based on our extensive previous experience, we have already established safety limits for an interim measure of renal function (GFR drops below 45) that could result in temporary or permanent discontinuation of individual subjects in the unlikely event that these limits are exceeded.

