This design is a two-armed clinical trial, with replicate measures at three time points: baseline, three, and six months. Since subjects are randomized to either WL-Control or WL-Protein arm, and the groups are presumed equal at baseline, the analysis is straightforward. Following the Good Clinical Practice Guidelines for the analysis of a clinical trial, we will employ mixed models, analyze under an Intent to Treat (ITT) criteria, and control for baseline and assess the impact of Time, Treatment Group and the interaction of these variables on the outcomes. Relative to the usual repeated measures designs, mixed models have several advantages: 1) missing values present no particular difficulties in estimation and the estimates are unbiased as long as the set of variables leading to MAR are estimated, 2) the usual assumption of conditional independence (compound symmetry) used in standard repeated measures need not be made, and 3) the actual times of measurement need not be equivalent across subjects. Controlling for the individual baseline values for the particular outcomes, the trajectories over time and differences in those trajectories will be assessed. Following the statistical principles section from the International Conference on Harmonization, we will select covariates (e.g., age, race, number of comorbidities) for the primary models a priori, but we also will conduct auxiliary sensitivity analyses that evaluate whether potential group imbalances bias the treatment effect estimate. These analyses will be performed using conventional testing for confounding. We note that we have listed numerous measures to be analyzed as outcomes, but have listed only 1 primary outcome (physical function, Aim 1).

For any particular outcome, the general form of the model will be:

$$Y_{it} = \beta_0 + \beta_1(\text{group}) + \beta_2(\text{time}_t) + \beta_3(\text{group} * \text{time}_t) + \beta_4(\text{covariates}) + \epsilon_{it}$$

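### The only stated group-level safety check compares the overall event rate with an unstated historical rate; no comparison between the randomised arms is provided for

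*Combined protocol and SAP*

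**What the plan says.** The section Data and Safety Monitoring sets up an internal advisory group that receives annual enrolment reports and "regular reports of any adverse events that occur". Its one stated comparison is to review clinical events "to identify any excess event rate in the study population over that expected based upon historical experience". No arm is named, no expected rate is given, and no size of excess is defined.

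The Adverse Events section separately says, "based on our prior experience with a similar (non-Veteran) population", that adverse events are anticipated but should not be associated with the intervention. It gives no rate either.

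A concurrent comparator exists. The Design section says: "An equal number of participants will be randomized across the two arms". The analysis plan for Aims 1 and 2 builds on this ("Since subjects are randomized to either WL-Control or WL-Protein arm"), but only for the efficacy and functional outcomes. None of the three analysis plans (Aims 1 and 2, Aim 3, supplemental protocol) contains an adverse event analysis.

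The other safeguards act on single participants or events:
- a GFR limit for individual subjects (Data and Safety Monitoring);
- extra renal testing for those with GFR of 45 to 59 (Exclusion Criteria);
- real-time review, with severity and relationship to the study assigned by the PI (Data and Safety Monitoring);
- notification of a data safety monitoring board (Risk/Benefit Assessment), with no comparison described.

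**The concern.** The safety question specific to this trial is whether the higher-protein diet causes more events than the control diet. Randomisation supplies a comparator with the same population, follow-up and method of event collection. The stated review instead relies on an outside expectation that is not quantified.

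Two features of the plan make the accuracy of that expectation uncertain. Participants enrolled after 10/1/2023 are followed for 3 months instead of 6. A per-participant rate taken from a longer study would be too high for them, which is the direction that hides harm. Also, the Power Estimate says that the earlier MEASUR-UP study used the same diets. If that study is the historical experience, which the document does not say, the benchmark already contains higher-protein participants.

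An excess confined to one arm might then raise no flag, or a generally higher event rate in this population might be read as a signal when the diets do not differ.

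**Working it through.** **Nothing to reproduce.** The plan gives no historical event rate, threshold or error level for safety. All event rates below, and the one-sided 0.05 level, are assumptions. The arm sizes come from the Design section: 112 completers, or 56 per arm, and the stated 84 per arm. Both are used as a range.

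**Step 1: effect of combining the arms.** With 1:1 allocation, overall rate = (control rate + protein rate)/2. For 10% and 20% this is 15%, so a 10-point excess in one arm appears as 5 points overall. This alone does not make the check weak. The overall check uses twice the sample of one arm, and a fixed benchmark has no sampling error.

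**Step 2: the two checks.**
- *Overall against historical:* flag if the total count X among 2n participants reaches the smallest r with P(X ≥ r | 2n, historical rate) ≤ 0.05. For 2n = 112, r is 11, 18, 24 and 31 at historical rates of 5%, 10%, 15% and 20%. For 2n = 168, r is 14, 24, 34 and 43. The chance of a flag is the exact probability that the sum of two binomials, one per arm, reaches r.
- *Between arms:* one-sided Fisher exact test and one-sided pooled z test, with power summed over all pairs of binomial counts.

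**Step 3: chance of a flag at the final sample size.**

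| Historical | Control | Protein | Overall rate | 56 per arm: overall check | 56: Fisher / z | 84 per arm: overall check | 84: Fisher / z |
|---|---|---|---|---|---|---|---|
| 10% | 10% | 20% | 15% | 41% | 35% / 43% | 64% | 49% / 58% |
| 15% | 10% | 20% | 15% | 4% | 35% / 43% | 4% | 49% / 58% |
| 20% | 10% | 30% | 20% | 3% | 80% / 86% | 4% | 93% / 96% |
| 10% | 5% | 20% | 12.5% | 15% | 72% / 81% | 27% | 88% / 92% |
| 10% | 15% | 15% | 15% | 41% (false alarm) | 3% / 5% | 63% (false alarm) | 3% / 5% |
| 5% | 5% | 10% | 7.5% | 22% | 15% / 28% | 38% | 24% / 35% |
| 10% | 5% | 10% | 7.5% | 0.2% | 15% / 28% | 0.2% | 24% / 35% |

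**Step 4: reading the table.**
- Accurate benchmark (rows 1 and 6): the overall check performs about as well as the between-arm test.
- Benchmark above the true control rate (rows 2, 3, 4 and 7): the overall check loses most or nearly all of its sensitivity. Row 2 is also what would arise if the historical experience came equally from both diets with the same true rates, since (10% + 20%)/2 = 15%. The chance of a flag then stays near the false-alarm level.
- Benchmark below the true rate in both arms (row 5): frequent false alarms with no diet effect.

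**Step 5: precision of a between-arm estimate.** For 10% versus 20% with 56 per arm, the 95% half-width is 1.96 × √(0.10×0.90/56 + 0.20×0.80/56) = 1.96 × √(0.25/56) = 0.131. The interval is about −3 to +23 points. The table by arm would be informative, but not decisive, for a modest difference.

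**The case against.** The strongest reply is that the text does not say that the arms are pooled. It speaks of the study population and leaves the report layout open, so reports could be split by arm in practice. That stands: the accurate statement is that review by arm is not provided for, not that it is ruled out.

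A reader might also infer several stronger points that the documents do not support:
- *That harm in one arm will be missed, or that combining the arms is itself the fault.* Rows 1 and 6 contradict this. The loss comes from a wrong benchmark, and the documents do not show that the benchmark is wrong, only that it is unstated.
- *That the benchmark is the non-Veteran experience.* The Adverse Events section cites that experience for what events to anticipate. It does not define the historical expectation used by the advisory group.
- *That renal harm depends on this check.* GFR has its own individual limit, extra testing in a defined range, and chemistries at each assessment in both arms. A severe fall would be picked up in the person concerned. What is missing is a comparison of GFR declines between arms.
- *That an excess could not be attributed to the diet.* Each event is graded for relationship to the study, and the plan describes no masking, so allocation can be retrieved. However, event-by-event judgement does not replace a comparison of arms when background events are expected in an older, impaired population.

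Finally, a between-arm test has low power for modest differences: 15% by Fisher for 5% versus 10% at 56 per arm. This stands, and it argues for estimates with intervals rather than a formal test.

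**Conclusion.** The concern holds in a limited form. The plan's only stated group-level safety comparison depends on a historical rate that it does not give, and it makes no provision for using the randomised control arm. If that rate lies above this trial's true control rate, an excess confined to the higher-protein arm can go unflagged (3% against 80% in the most marked example at 56 per arm). If it lies below the trial's true background rate, false alarms can arise (41% against 3%). If it is accurate, little sensitivity is lost.

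These sizes rest on assumed event rates, an assumed one-sided 0.05 rule, and a single look at the final sample size. Annual reviews would have fewer events. Individual GFR limits and attribution by the PI limit the consequences but do not compare the arms. This is a cheap improvement to a low-risk trial, not a failure of safety oversight.

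**What to change.** In the regular reports to the advisory group, add one table by randomised arm. It should give counts and rates of adverse events, serious adverse events and GFR declines, with the between-arm difference and its 95% confidence interval. Present it descriptively, without a formal test. State the historical rate, its source and its length of follow-up, and keep it as a secondary reference beside the overall rate.

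The cost is one more table per report, from data already collected. The study statistician should prepare it, and the advisory group should review it without outcome assessors present. That needs a short separate part of the meeting, because the group otherwise meets with the investigators. No individual GFR or discontinuation rule changes.
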